#### 10.2.2 Justification of the sample calculation

Although there are no references on the calculation of the sample size in phase I studies, it was considered pertinent to perform it according to the safety results of a phase I study, carried out with three ocular lubricants (Humylub Ofteno® PF, Xyel® Ofteno and Systane® Ultra). [53]

The reference study was a single-center, randomized, 1: 1: 1, parallel group, blinded clinical trial. In total, 30 ophthalmologically and clinically healthy subjects were enrolled and included in the safety analyzes.

PRO-037 (Lagricel® Ofteno, multi-dose) is expected to be not inferior to its comparator (Lagricel® Ofteno, single-dose), based on the following working hypotheses:

$$H_0: \varepsilon > \delta$$

$$H_0: \varepsilon \leq \delta$$

Where  $\mu A - \mu B = \epsilon$ , the true difference of the means between the test treatment (Lagricel® Ofteno, multi-dose) and the active control (Lagricel® Ofteno unit-dose). Where  $\delta$  is the margin of non-inferiority, and the relationship between the sample sizes of the two groups is given by:

$$k = \frac{n_A}{n_B}$$

The calculations were made using the equation for two proportions, considering a power of 80% ( $\beta$ ), a significance level of 0.05 ( $\alpha$ ) and a non-inferiority margin ( $\delta$ ) of 5%. [54]

$$n_B = (\frac{p_A(1-p_A)}{k} + p_B(1-p_B))(\frac{z_{1-\alpha} + z_{1-\beta}}{k})^2$$

$$p_A - p_B - \delta$$

In the reference study, after 10 days of treatment (1 drop / 4 times a day), 28 AE were reported in 14 subjects out of a total of 30 subjects exposed to any of the three interventions (46.67%). Without observing statistical differences in the incidence of AE between the three treatment arms (p = 0.788), 19 of the AE were ocular, where burning was the most common, followed by pruritus. Other ocular AE reported were discharge, SCE, and dry eye sensation.

The percentage of ocular AE reported in the study was considered, with respect to the total AE for the three treatments. As it is an ocular lubricant, a similar proportion of ocular AE is expected in ophthalmologically and clinically healthy subjects (50%).

The calculated sample was 56 eyes (28 eyes / arm; 14 subjects / arm), increasing the calculation by 20% considering possible losses, 17 subjects / arm (both eyes) are estimated.

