#### 10.1.4 Deviations from the statistical analysis plan

According to the calculation of the sample size to meet the objective of the study, 34 evaluable subjects (17 subjects per arm / both eyes) are required. If this number is not met due to the loss of subjects greater than 20% contemplated in this protocol (loss of follow-up or withdrawal of ICF), in order to balance the treatment groups, the sponsor may substitute these subjects.

The results obtained from the substituted subjects will continue to be used for the safety analysis and will be part of the ITT.

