#### 10.2 Calculation of sample size

#### 10.2.1 Number of subjects calculated

n = 34 evaluable subjects (both eyes) 17 subjects per arm. 17 subjects (both eyes) are estimated per treatment arm.

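### The stated 28 eyes per arm does not follow from the plan's own formula, which needs about 1,237 per arm at equal 50% rates; power for the 5-point margin is about 10%, not 80%

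*Combined protocol and SAP*

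**What the plan says.** Section 10.2.2 frames the comparison as non-inferiority of the multi-dose product to the single-dose product. On method it says: "The calculations were made using the equation for two proportions, considering a power of 80" per cent, with "a significance level of 0.05" and a non-inferiority margin of 5%. The printed formula uses the normal quantile at 1 − alpha, so the test is one-sided.

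The rates come from a reference study of three lubricants: 28 AEs in 14 of 30 subjects (46.67%), of which 19 AEs were ocular. For this trial the section says "a similar proportion of ocular AE is expected in ophthalmologically and clinically healthy subjects (50" per cent). It gives no separate values for the two arms, no expected true difference and no correlation between the two eyes of a subject.

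The result reads: "The calculated sample was 56 eyes (28 eyes / arm; 14 subjects / arm), increasing the calculation by 20% considering possible losses", giving 17 subjects per arm. Section 10.2.1 restates this as "n = 34 evaluable subjects (both eyes) 17 subjects per arm". Section 10.1.4 says: "According to the calculation of the sample size to meet the objective of the study, 34 evaluable subjects" are required. The synopsis (1.1) also calls the 34 evaluable.

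**The concern.** A 5-point margin around a 50% event rate is a demanding target, because the variance of a proportion is largest at 50%. Sample sizes for such a target normally run to hundreds or thousands per arm, so 28 eyes per arm cannot be right without some further assumption that the section does not state.

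AE incidence is a primary outcome. Section 10.1.5 would declare the product safe and effective if no clinical and statistical differences appear in the primary outcomes. With so few subjects, a non-significant AE difference is likely even if a sizeable one exists. The 80% power statement is what would make such a result look reassuring. An ethics committee or regulator reading 10.2.2 would be misled about what 34 healthy volunteers can establish.

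**Working it through.** **Inputs (section 10.2.2 unless noted)**

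- One-sided alpha 0.05: z = 1.6449
- Power 80%: z = 0.8416
- Margin δ = 0.05
- AE proportion 50%, expected to be similar, so pA = pB = 0.50
- Equal arms (10.2.1), so k = 1
- Losses 20%

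**Step 1. The plan's figure**

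n_B = [pA(1 − pA)/k + pB(1 − pB)] × [(z₁₋α + z₁₋β)/(pA − pB − δ)]²

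= (0.25 + 0.25) × (2.4865/0.05)² = 1,236.5, so **1,237 per arm** (2,474 in total).

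The plan states 28 per arm; 1,237/28 ≈ 44. The stated figure is not reproduced.

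**Step 2. Nearby readings**

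| Reading | n per arm |
|---|---|
| Both arms 46.67% (14/30) | 1,232 |
| Both arms 67.9% (19/28) | 1,079 |
| Both arms 50%, one-sided alpha 0.025 | 1,570 |
| Superiority, 50% vs 55%, one-sided | 1,233 |
| Superiority, 50% vs 55%, two-sided | 1,565 |

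None is near 28.

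**Step 3. A possible origin of 56**

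Take pA = 0.50 and pB = 19/28 = 0.679:

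(0.25 + 0.2181) × (2.4865/0.2286)² = 55.4, so 56.

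This matches the printed total, but the text does not say it was done, so it is an inference. If it was done, three problems follow:

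- n_B is the size of one arm, so 56 should not have been split into 28 and 28.
- It assumes about 18 points fewer AEs on the test product, against the expectation of a similar proportion and a formulation that 2.2.4 calls identical.
- 19/28 is the share of events that were ocular, not a risk per subject or per eye.

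**Step 4. Power at the stated sizes**

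Power = Φ(0.05/√(0.5/n) − 1.645), with 50% in both arms.

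| Unit and n per arm | Power for the 5-point margin | Margin with 80% power |
|---|---|---|
| 28 eyes, independent | 10.2% | 33 points |
| 34 eyes, independent | 10.9% | 30 points |
| 17 subjects | 8.8% | 43 points |
| 14 subjects | 8.4% | 47 points |

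The two eyes of a subject are correlated, so with 17 subjects per arm the power lies between 8.8% and 10.9%. On the Step 3 reading, 28 per arm has 55% power.

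**Step 5. Precision**

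With 17 subjects per arm at 50%, the 90% interval half-width is 1.645 × √(0.5/17) = 1.645 × 0.1715 = 0.282, or about 28 points. For the upper limit to fall below +5 points, the observed AE rate on the test product would have to be about 28 − 5 = 23 points lower than on the comparator.

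**Step 6. Losses**

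14 × 1.2 = 16.8, so 17; this step reproduces. It means that 17 per arm already contains the allowance and that 14 per arm (28 in all) is the evaluable target. A 20% loss from 34 leaves 34 × 0.8 = 27.2, about 27, just under 28. To keep 14 after a 20% loss needs 14/0.8 = 17.5, so 18 per arm.

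**The case against.** Five points can be made for the plan.

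- **Equal rates are not written down.** The section never states pA = pB = 0.50, so 1,237 and 10% are conditional. This is true, and the condition should be stated. But it is the natural reading of a similar proportion for an identical formulation, and the only alternative found that yields 56 still does not support 28 per arm.
- **The planned tests are difference tests.** Sections 10.1.2 and 7.3.3 use chi-square, Fisher or Mann-Whitney, and the hypotheses in 2.3.4 are similar against different. Non-inferiority and the 5% margin appear only in 10.2.2. So the 10% is the power of the design described in 10.2.2, not of the decision rule in 10.1.5, and the 23-point figure uses an interval criterion the plan does not contain. This qualification stands. It does not rescue the section, because the 80% claim is made for exactly that design.
- **Phase I trials need no formal power.** Section 2.4.2 justifies a small sample by the phase, and 10.2.2 notes the lack of references for phase I sizing. That supports keeping 34 subjects. It does not support stating a power that the trial does not have.
- **The reconstruction of 56 is inference.** It is, and the finding does not depend on it.
- **The loss and evaluable point is small.** Dividing by 0.8 rather than multiplying by 1.2 changes one subject per arm, and 5.3.1 and 10.1.4 allow substitution. The point is minor, but the label is inconsistent, and 10.1.4 ties substitution to this number.

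**Conclusion.** Section 10.2.2 is wrong as written. With one-sided alpha 0.05, a 5-point margin and equal true rates of 50%, 80% power needs 1,237 independent observations per arm, about 44 times the 28 stated. Power with the stated numbers is about 9% to 11%, depending on whether subjects or independent eyes are counted. If 50% against 19/28 was intended, the requirement is 56 per arm and 28 per arm has 55% power. No reading supported by the text gives 80% at 28. The use of the word evaluable for all 34 subjects is a lesser inconsistency.

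**What to change.** Keep 34 subjects and correct the text:

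1. In 10.2.2, delete the claim of 80% power for a 5% margin and the derivation of 56 eyes.
2. Replace it with wording along these lines: The sample of 17 subjects per arm is a feasibility and precision choice for a phase I tolerability study. At an AE rate of 50% in both arms, it gives a 90% confidence interval half-width of about ±28 percentage points for the difference, and about 9% power for a 5-point non-inferiority margin (one-sided alpha 0.05). The AE comparison is therefore one of estimation.
3. In 1.1, 10.1.4 and 10.2.1, say whether 34 is the number randomised or the number evaluable. If 34 are randomised, about 27 are evaluable at 20% loss. Word the substitution rule in 10.1.4 to match.

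The cost is wording in 1.1, 10.1.4 and 10.2, with no extra subjects or visits. The stated power becomes much less favourable, and a finding of no difference in AEs can no longer rest on it.

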#### 2.6.1.3 Dosage of Investigational Products

One drop four times a day, both eyes, for 7 days.

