### 7.2 Randomization and Blinding

Subject randomization will be carried out using a computerized assignment system. After signing the FCI, the patient will receive a patient number with which all their information will be coded pseudo anonymously during collection and completely anonymized during analysis.

The generation will be carried out by a third party, authorized by Sophia Laboratories S.A. of C.V., through its electronic system. The information for this third party will be in the file.

Although it is an open study, the secondary container will be masked.

PIs will be identified by means of labels in accordance with current and applicable regulations, they must contain at least:

- Name, address and telephone number of the sponsor.
- Pharmaceutical form and route of administration.
- Lot Number.
- Legend "Exclusively for clinical studies"
- Date of Expiry.

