#### 7.3.3 Definition of variables, methods and scales to be used for their measurement

Variable	Туре	Unit (Symbol)	Method of measurement	normal value	evaluation time	statistical test
Primary						
Adverse events	Discreet	Number of cases (n)	Counting	0	VB, V1, VF y LLS	U de Mann- Whitney
events	Categoric al nominal	Present/ absent	Observation	Absent	LLS	χ2 or exact by Fisher
Score of	Discreet	Points	Questionnaire	NA	VB, VF	U de Mann- Whitney
Secondary						
MAVC	Discreet	Fraction	Poster of Snellen	1	VB, V1 y VF	U de Mann- Whitney
Corneal and conjunctival fluorescein staining	Ordinal	Levels	Direct observation with slit lamp and cobalt blue filter, Oxford scale graduation	0	VB, V1 y VF	χ2 or exact by Fisher
Corneal and conjunctival staining with lysamine green	Ordinal	Levels	Direct observation with slit lamp, Oxford scale graduation	0	VB, V1 y VF	χ2 or exact by Fisher
Conjunctiv al hyperemia	Ordinal	Normal / Very Mild / Mild / Moderate / Severe	Direct observation. Clasification of Efron.	Normal	VB, V1 y VF	χ2 or exact by Fisher
Chemosis	Categorical nominal	Present / absent		Absent	VB, V1 y VF	χ2 or exact by Fisher

Table 2. Defoperational definition of variables

The variables, the method and scales for their measurement are described in detail below. They are in order according to Table 2

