#### 7.3.3.3 Best Corrected Visual Acuity

Visual acuity (VA) is a test of visual function. Spatial AV is the ability to distinguish separate elements of an object and identify them as a whole. It is quantified as the minimum angle of separation (located at the nodal point of the eye) between two objects that allows them to be perceived as separate objects.

Snellen's notation is described as the distance at which the test is performed, divided by the distance at which the letter is vertically equal to 5 arc minutes. Thus, at 6 meters a letter 6/6 (20/20) is equivalent to 5 arc minutes, a letter 6/12 (20/40) is equivalent to 10 minutes, and a letter 6/60 (20/200) is equivalent to 50 minutes. The Snellen fraction can also be expressed as a decimal (that is, 20/20 = 1 and 20/40 = 0.5). [41]

VA will be evaluated baseline, without refractive correction with the Snellen chart. Which will be located in a place with adequate natural or artificial lighting and at a distance of 3m from the subject to be evaluated. The visual acuity of each eye will be taken, starting with the right eye (OD) asking the subject to keep both eyes open and using an occluder to cover the left eye (OS); The subject will read aloud the lines that the evaluator indicates, the line of smallest letters that can be seen will be noted by the evaluator in fraction as the VA of OD in the clinical record. The OS is proceeded with the same method.

Subsequently, the subject's objective and subjective refractive correction will be carried out. The result of the subjective refraction will be reported as BCVA, it will be noted in fraction in the clinical record and in the FERC, also in the FERC it will be noted in decimal. By definition, BCVA cannot be lower than VA.

Handling as EA: a decrease of more than 2 lines in the Snellen chart should be reported and handled as EA.

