#### 7.3.3.4 Corneal and conjunctival fluorescein staining

A drop of topical anesthetic will be instilled in the conjunctival cul-de-sac, then a second drop will be applied to the tip of the fluorescein strip allowing it to settle on the strip for 5 seconds to elute the dye, shaking off the excess at the end. A small contact of the strip with the conjunctiva is made in the temporal cul-de-sac, while the patient looks up, without damaging the conjunctiva. It will be graded according to the Oxford scale. [42]

The IP will record in the file and the FERC the grade awarded for fluorescein staining of OD and OS respectively.

Management as AE: corneal stains that are equal to or greater than grade III will be considered as AE.

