#### 10.1.2 Interpretation of data

The Kolmogorov-Smirnov tests will be carried out to know if the distribution presents normality in the results obtained in each study group. [fifty]

The results of the continuous quantitative variables will be presented in measures of central tendency: mean, standard deviation and ranges.

The statistical analysis of the continuous quantitative variables to find significant differences (p < 0.05) will be as follows:

- Intra-group analysis: they will be determined using the Wilcoxon rank test for quantitative variables. [51]
- •
- Between-group analysis: The differences between the groups will be analyzed using the Mann-Whitney U test.

The level of difference to consider significance will be an alpha ( $\alpha$ ) of 0.05 or less.

The result of the nominal and ordinal qualitative variables will be presented in frequencies, proportions and percentages.

The statistical analysis to identify significant differences of the qualitative variables will be carried out by creating 2x2 contingency tables and will be carried out as follows:

- Intragroup difference: McNemar test. [52] Which is applied to 2 × 2 contingency tables with a dichotomous trait, with pairs of matched subjects, to determine if the marginal frequencies of row and column are equal (marginal homogeneity).
- Difference between groups: Pearson's Chi-square test (X2) or Fisher's exact test in expected values less than 5.

The level of difference to consider significance will be an alpha ( $\alpha$ ) of 0.05 or less.

For the reporting of adverse events, all the eyes of those participants who were randomly assigned to an intervention group after the baseline visit will be considered. The results will be expressed in number of subjects.

The final report of the results will be shown in tables or graphs, as appropriate.

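### The sample size counts each eye as an independent unit although subjects are randomised, and the secondary eye measures have no unit of analysis or two-eye rule

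*Combined protocol and SAP*

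**What the plan says.** **Sizing (section 10.2.2).** The calculation uses a two-proportion non-inferiority formula with 80% power, alpha 0.05, a 5% margin and an expected ocular AE proportion of 50%. The result is "The calculated sample was 56 eyes (28 eyes / arm; 14 subjects / arm"), raised by 20% to 17 subjects per arm. The input comes from a reference study in which "28 AE were reported in 14 subjects out of a total of 30 subjects exposed to any of the three interventions"; 19 of the 28 AEs were ocular.

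**Assignment and treatment.** Section 7.2: "Subject randomization will be carried out using a computerized assignment system". Section 2.6.1.3: "One drop four times a day, both eyes, for 7 days". The two eyes of a subject therefore always share an arm.

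**Unit for AEs (section 10.1.2).** All eyes of randomised participants are considered, but "The results will be expressed in number of subjects".

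**Secondary eye measures.** For acuity, "The visual acuity of each eye will be taken" (section 7.3.3.3). For fluorescein staining the record holds "the grade awarded for fluorescein staining of OD and OS respectively" (section 7.3.3.4), and section 7.3.3.5 likewise calls for a grade for each eye with lissamine green. The variables table in section 7.3.3 gives a method for each measure (for fluorescein, "Direct observation with slit lamp and cobalt blue filter, Oxford scale graduation") and a test: Mann-Whitney for acuity, chi-square or Fisher for staining, hyperemia and chemosis. Section 10.1.2 adds Wilcoxon and McNemar within groups. Neither place says whether the unit is the eye or the subject, or how two eyes become one value.

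**The concern.** Two eyes of one person, given the same drops, are not two independent observations. Halving an independent-unit count to obtain subjects is right only if the between-eye correlation is zero. The plan neither states nor defends that assumption, and it conflicts with the plan's own decision to report AEs in subjects. The input rate does not support an eye count either: 14 of 30 is a proportion of subjects, and 19 of 28 is a proportion of events.

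Two things are at stake. First, the trial delivers less information than section 10.2 implies. This matters because section 10.1.5 concludes in the product's favour when no difference is found in the primary outcomes, so overstated information makes that conclusion look better supported than it is. Second, for the secondary measures an analyst could test 34 eyes or 17 subjects per arm and comply with the plan either way. Testing eyes as independent can make p-values too small.

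**Working it through.** **1. The plan's own figure.** Inputs from section 10.2.2: expected proportion 0.50 (taken for both arms, since no separate values are given), margin 0.05, one-sided alpha 0.05, power 80%, 1:1 allocation.

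- n per arm = [p(1−p) + p(1−p)] × ((z for alpha + z for power)/margin)² = 0.5 × ((1.645 + 0.842)/0.05)² ≈ 1,237.
- The stated 28 is not reproduced. That is a separate point; below, 28 is taken as given to isolate the unit error.
- The later steps do reproduce: 28/2 = 14, and 14 × 1.2 = 16.8, rounded to 17.

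**2. Units available for the sizing outcome (no assumption needed).** AEs in subjects give 14 units per arm, or 17 with the loss allowance, against 28 calculated.

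**3. Design effect for two eyes per subject.** DE = 1 + (2 − 1)ρ = 1 + ρ, where ρ is the between-eye correlation. The documents give no value, so ρ is an assumption. Subjects per arm = 28(1 + ρ)/2.

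| ρ (assumed) | Subjects/arm before losses | × 1.2 | Independent units in 34 eyes, 34/(1+ρ) |
|---|---|---|---|
| 0 | 14 | 17 | 34.0 |
| 0.25 | 17.5 → 18 | 22 | 27.2 |
| 0.5 | 21 | 26 | 22.7 |
| 0.9 | 26.6 → 27 | 33 | 17.9 |
| 1 | 28 | 34 | 17.0 |

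Only the first row matches the plan. The row for ρ = 1 is equivalent to one result per subject, which is how AEs are reported.

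**4. Precision at the plan's 50% rate.** 95% half-width of a difference = 1.96 × √(0.5/n).

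- n = 17 subjects: ±33.6 points. n = 34 independent eyes: ±23.8 points.
- Before the loss allowance, n = 14: ±37.0 points. n = 28: ±26.2 points.

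**5. Error rate if the secondary measures are tested per eye.** Normal approximation for a nominal two-sided 5% test: 2 × (1 − Φ(1.96/√(1 + ρ))) = 11.0%, 14.4% and 15.5% at ρ = 0.5, 0.8 and 0.9.

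Simulation: 17 subjects × 2 eyes per arm, no true difference, 20,000 runs, the plan's chi-square test or Fisher when an expected count is below 5. Here ρ is the correlation of the observed yes/no signs.

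| Per-eye test | ρ 0.5 | ρ 0.8 | ρ 0.9 |
|---|---|---|---|
| Sign in 5% of eyes | 1.4% | 2.8% | 3.5% |
| Sign in 10% | 5.1% | 8.3% | 9.9% |
| Sign in 20% | 10.7% | 14.8% | 16.1% |
| Sign in 50% | 11.1% | 14.1% | 15.9% |
| Mann-Whitney, continuous score | 10.7% | 14.0% | 15.9% |
| Mann-Whitney, 3-level score* | 9.6% | 12.6% | 13.9% |

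*For the 3-level score ρ is on the underlying scale; the observed correlations were 0.40, 0.64 and 0.75.

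Mann-Whitney on one value per subject (mean or worst eye) held 4.7 to 5.1% throughout.

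**The case against.** **The primary comparisons already use the subject.** AEs are reported in subjects, the ICO is one questionnaire per subject, and the decision rule in section 10.1.5 uses only the primary outcomes. This stands. No inflation is claimed for the primary tests. It also shows that the eye count in the sizing disagrees with the analysis.

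**The design-effect figures adjust a number that is itself unsupported.** This also stands. The 21 to 27 subjects per arm show the size of the unit error alone; they are not a requirement for any stated power. A recalculation that still counted eyes would repeat the error.

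**The ±24 points are not in the plan.** Correct. The plan states no precision; ±24 is what its eye count would imply.

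**The correlation is assumed, and its scale matters.** At 0.25 the need is 18 subjects per arm, still above 14. Outcomes are mostly changes from baseline, whose between-eye correlation may differ from that of levels. With ρ = 0.5 on an underlying continuous scale, a 4,000-run simulation of the per-eye chi-square/Fisher rule gave 0.5%, 3.4%, 8.7% and 8.5% at sign rates of 5, 10, 20 and 50%. At 0.9 it gave 13 to 14% at rates of 20 to 50%. The inflation is smaller on that scale but does not disappear for common signs.

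**Healthy subjects may show few signs, and the only secondary Mann-Whitney is for acuity, a coarse scale.** For rare signs the objection is right: there is no inflation. For a coarse acuity-like score the per-eye Mann-Whitney still ran at about 9 to 14%. A false positive here would be a spurious safety difference on a secondary measure, not a false claim of safety.

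**Conclusion.** The concern holds. As written, the sample size rests on units that the design does not have: subjects are randomised and AEs are counted in subjects, so there are at most 17 units per arm, not 28 or 34. This part needs no assumption. How many more subjects would be needed, and how far per-eye tests would be inflated, depend on a between-eye correlation that the documents do not give; 0.5 to 0.9 is an illustrative range. The inflation also depends on the analyst choosing eyes as the unit, which the plan neither requires nor prevents, and it is absent for rare signs. The primary tests are not shown to be affected. This should be fixed before analysis. Confidence is high on the unit error and the missing rule, lower on the exact size of the consequences.

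**What to change.** - **Sections 7.3.3 and 10.1.2:** name the subject as the unit of analysis and add a unit column to the variables table. For AEs, a subject with an event in either eye counts once, with subjects as the denominator. For staining, hyperemia and chemosis, use the worst eye per subject. For acuity, use the mean of both eyes or the worst eye, chosen in advance.
- **Alternative:** keep both eyes in a GEE or mixed model clustered on subject, with a small-sample correction because there are only 17 clusters per arm. The choice between this and one value per subject is a matter of preference; fixing it beforehand is not.
- **Section 10.2:** drop the eye count, restate the sample in subjects, and give the power or precision that 17 subjects per arm deliver (about ±34 points at a 50% rate).

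The cost is wording only, with no new data and no added enrolment. The downside is that the stated information becomes visibly weaker. Correcting the unit does not by itself repair the justification, because 28 per arm still does not follow from the stated 50% rate and 5% margin.
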